3.5.2.3. Hematopoietic growth factors

Hematopoietic growth factors are not permitted during study treatment. The patient should be referred to a hematologist for further evaluation (1) if frequent transfusions are required or (2) if the treatment-related hematologic toxicities have not recovered to CTCAE Grade 1 or less after 4 weeks.

3.6. Removal/Replacement of Patients from Therapy or Assessment

3.6.1. Screen Failures

All patients must continue to meet the inclusion and exclusion criteria up to and including the first day of treatment. Reasons for patients who have enrolled, but become ineligible could include (but are not limited to):

- The patient is no longer eligible based on laboratory parameters
- The patient's performance status has declined

- The patient no longer has measurable disease

Patients who become ineligible prior to initiation of therapy per protocol will be considered screen failures. Screen failures must be replaced until 50 patients with advanced HR+/HER2- breast cancer are enrolled.

3.6.2. Evaluable Patients

3.6.2.1. Objective Response Evaluable

To be considered evaluable for the primary endpoint of ORR as determined by RECIST v1.1, the patient must meet all inclusion/exclusion criteria and remain on study treatment at least until the first re-staging after cycle 2 of SM-88 used with MPS unless they are taken off for disease progression, clinical progression, or death related to the underlying solid tumor malignancy (as determined by the treating oncologist) in which case they **will be** deemed evaluable. However, patients who have initiated therapy and who withdraw from the study for any reason other than clinical or radiographic progression, or death believed unrelated to their underlying solid tumor malignancy **will not be** considered evaluable for response. Reasons for patients who have initiated therapy, but are no longer evaluable for response could include (but are not limited to):

- The patient cannot tolerate therapy despite dose modifications, and there is no evidence of clinical/radiographic disease progression at the time of stopping therapy
- An unexpected and/or unrelated medical illness, such as a stroke or myocardial infarction that is considered unrelated to the underlying solid tumor malignancy
- An unexpected trauma or death that is considered unrelated to the underlying solid tumor malignancy

If a patient is deemed to be non-evaluable for the primary endpoint of ORR they will be replaced.

3.6.2.2. Safety/Tolerability Evaluable

Any patient who receives at least one dose of SM-88 and/or MPS will be evaluable for safety and tolerability as measured by NCI CTCAE v5.0.

3.7. Multicenter Trial Management

3.7.1. Personnel

At each site, personnel dedicated to this protocol will be:

- A study PI
- A research coordinator
- A data manager

In addition, Georgetown University's Multicenter Project Management Office will oversee the conduct of the trial at Lombardi-Georgetown and additional sites. Georgetown University's Multicenter Project Management Office will be the main point of contact for [name] and the other site PIs for any study related concerns, including data management and regulatory.

3.7.2. Patient Enrollment

Enrollment at the sites will be competitive. If a patient is being screened for enrollment, the local research coordinator must send an email containing the patient's initials to the local PI, to [name], and to the Georgetown University's Multicenter Project Management Office. If a patient is successfully screened, the local research coordinator must send all supporting documentation to Georgetown University's Project Management Office by secure email to confirm eligibility. Patients should not start therapy until [name] and Georgetown University's Project Management Office have reviewed the patient's records and confirmed that the patient is indeed eligible for enrollment.

3.7.3. Data Collection and Management

Patient data will be entered into the on-line accessible database. This database is housed at Lombardi-Georgetown, but is accessible anywhere there is internet access. The data manager and research coordinator at each site will attend an on-line training session (if not done previously) so that they may learn how to enroll data into the database. All screening data should be entered prior to starting therapy, and all ongoing patient data should be entered within 10 business days of each patient visit.

3.7.4. Conference Calls

A monthly conference call will be held between Lombardi-Georgetown and the other sites. Lombardi-Georgetown will conduct the conference call to review screening and enrollment metrics, participant milestone dates, troubleshoot study challenges, and answer site questions. Site PI, participating investigators, study coordinators and data managers may attend. At least one site representative should attend each call.

3.7.5. Trial Auditing

Georgetown University's Multicenter Project Management Office will arrange all primary source documents for the patients to be audited. This will include collecting copies of the primary source data for any patients treated at other sites.

4. Study Procedures

4.1. Study Procedures

The study-specific assessments are detailed in this section are outlined in Table 3.

Thirty patients will be enrolled in first stage of the study, and if 3 or more patients have an objective response (complete or partial response) then an additional 20 patients will be enrolled in the second stage of the study. Patients will receive the recommended phase 2 dose (RP2D) of SM-88 (460 mg by mouth [PO] twice a day [BID] D1 – 28) as well as three conditioning agents (MPS): methoxsalen (10 mg PO daily [Qd] D1 – 28), phenytoin (50 mg PO Qd D1 – 28), and sirolimus (0.5 mg PO Qd D1 – 28).

[figure not shown]

Figure 1. Study design

Patients will be evaluated, including physical exam and laboratory testing, every 4 weeks on Day 1 of each cycle. Laboratory testing will be performed every 2 weeks for the first 2 cycles and then on Day 1 of each subsequent cycle. Restaging scans will occur every 8 weeks (+/- 7 days) to evaluate for objective response. For patients who achieve a complete response (CR), partial response (PR), or stable disease (SD) confirmed on two consecutive restaging scans by RECIST v1.1 criteria, restaging scans may transition to every 12 weeks. Scans will occur as per this schedule determined by the calendar and not the cycle number. However, if there are any significant delays, restaging exams should not occur more than 12 weeks apart (+/- 7 days). Patients will continue to remain on study as long as there is no evidence of PD (according to RECIST v1.1 criteria) and the therapy is adequately tolerated. Interim analyses to assess secondary endpoints of CBR, PFS, and DOR will be scheduled to occur at 12 months and 24 months.

[figure not shown]

Figure 2: Study Schedule

4.2. Treatment Regimen

The trial is designed to assess the efficacy of SM-88 used with MPS in patients with advanced HR+/HER2- breast cancer.

Potential trial patients will be pre-identified at participating centers.

Patients who have an adequate performance status (PS), hematologic, hepatic, and renal function will be screened for enrollment. Patients who ultimately meet the inclusion and exclusion criteria as detailed in Section 3, and desire participation, will be enrolled.

4.3. Patient Screening, Enrollment, and Monitoring Assessments

Screening scans and laboratories must be completed within 28 days prior to the first dose of investigational product. Any results falling outside of the reference ranges may be repeated at the discretion of the Investigator. Assessments performed for clinical indications (not exclusively to determine study eligibility) may be used for baseline values even if the studies were done before informed consent was obtained. Treatment or visit delays for public holidays or weather conditions do not constitute a protocol violation.

Assessments performed exclusively to determine eligibility for this study will be done only after obtaining informed consent. Signed informed consent will be obtained from the patient or the patient's legally acceptable representative before any study-specific procedures are undertaken. For procedures performed at screening and repeated, the later procedure performed prior to dosing, will serve as a baseline for clinical assessment. A complete history and physical will be obtained at the screening visit. Additionally, labs will be reviewed/ordered during the screening visit, prior to the initiation of therapy.

Patients who pass screening will again undergo a full evaluation on Cycle 1 Day 1, including a physical examination, vital signs, performance status, chemistry, hematology, serum or urine pregnancy test, medication review, and adverse event evaluation. If any abnormality is identified at patient assessment on Cycle 1 Day 1, prior to initiating therapy, the patient will be deemed a screen failure and will not start treatment.

The screening and monitoring procedures include the following listed below. Details are provided in Table 3.
Version 2.2 11/18/2022

4.3.1. Informed Consent

Signed informed consent will be obtained from the patient or the patient's legally acceptable representative before any study-specific procedures are undertaken.

4.3.2. Medical History

The following information should be collected during the Screening Period:

- 1) Complete medical history, including documentation of any clinically significant medical conditions
- 2) Presence and severity of any symptoms/conditions associated with their advanced solid tumor malignancy
- 3) Detailed oncology history, including:
 - a. Date of primary cancer diagnosis
 - b. Pathology (histology or cytology) of primary tumor
 - c. Metastasis information (including the location)
 - d. Surgical history
 - e. Anti-cancer and radiation treatments administered (including dates and type of modality, and if therapy was in the neoadjuvant, adjuvant, or metastatic setting)
- 4) At each visit, the patient's medical history will be reviewed and any changes from baseline will be recorded in the CRF. On Cycle 1 Day 1 any changes observed from the screening assessments, prior to dosing, will be recorded in the patient's medical history. All medications (prescription or over-the-counter, including vitamins and/or herbal supplements) will be recorded beginning with the Screening Visit and continuing up through the date of the off study visit
- 5) When available, also collect genomics,

4.3.3. Demographics

Age, gender, and self-reported race/ethnicity will be recorded.

4.3.4. Review patient eligibility criteria

See Section 3.2 (Inclusion criteria) and Section 3.3 (Exclusion criteria).

4.3.5. Review previous and concomitant medications

See Section 3.5.

4.3.6. Physical exam including vital signs, height, and weight

At screening, a physical examination, height, weight, blood pressure and pulse rate is required. Symptom-directed physical examinations, blood pressure, weight and pulse rate will be performed. All physical examinations and vital signs assessments should be performed by a physician or registered nurse or other qualified health care provider according to local regulations.

4.3.7. Performance Status (PS)

PS will be evaluated prior to study entry according to Table 7 in Appendix A.

4.3.8. Laboratory samples

Laboratory samples for this study will be assessed using the certified laboratory at the Investigators' institutions or at a clinical laboratory such as Quest or LabCorp and these data will be used for all data analysis. The Principal Investigator or sub-Investigator will review, initial and date all laboratory results. Any laboratory value outside the reference range that is considered clinically significant by the Investigator will be followed as appropriate. Clinically significant laboratory values will be recorded as adverse events if they meet the criteria as specified in Section 6.3.

4.3.8.1. Hematology

Hematology samples (complete blood count [CBC]) will be collected and assessed using a certified laboratory. The Investigator will review, initial, and date all laboratory results. Any laboratory value outside the reference range stated in the inclusion criteria will preclude the patient from study participation.

4.3.8.2. Serum chemistries

Comprehensive metabolic panel (CMP) to include: albumin, alkaline phosphatase, ALT, AST, blood urea nitrogen (BUN), creatinine, electrolytes (sodium, potassium, calcium, chloride, bicarbonate), glucose, and total bilirubin. Any laboratory value outside the reference range stated in the inclusion criteria will preclude the patient from study participation.

4.3.8.3. Lipid panel

Lipid panel to include: total cholesterol, low-density lipoprotein (LDL), high-density lipoprotein (HDL), and triglycerides. Laboratory values outside the reference ranges at an institution will not preclude the patient from participation in the study at the treating physician's discretion, but values will be followed throughout the study.

4.3.8.4. Pregnancy Test

For female patients of childbearing potential, a serum or urine pregnancy test will be performed at the Screening Visit and a serum or urine pregnancy test will be done at the Cycle 1 Day 1 visit prior to the first dose of study drug if > 14 days from screening pregnancy test. A female patient will not be eligible for enrollment if she has a positive serum or urine pregnancy test \leq 3 days prior to study drug administration, is breast-feeding, or is planning to conceive children within the projected duration of the study treatment. The test results must be reviewed and determined to be negative prior to dosing. If a urine pregnancy test is positive at Cycle 1 Day 1, it should be confirmed by a serum pregnancy test. Urine/Serum pregnancy tests for women of childbearing potential must be performed within 8 days of each subsequent cycle (approximately every 4 weeks) during treatment with study drugs. The test may be repeated more frequently at the discretion of the Investigator at any time during the study. Should a female study patient become pregnant or suspect she is pregnant while participating in this study, she should inform the treating Investigator immediately. The study PI [name] and TYME should be notified as well, as outlined in Section 6.7. If a patient becomes pregnant, or if a patient's spouse becomes pregnant while on trial, he or she will be removed from the study immediately.

Pregnancy testing does not need to be pursued in patients who are judged to be postmenopausal before enrollment, or who have undergone bilateral oophorectomy, total hysterectomy, or bilateral tubal ligation. Patients may be considered postmenopausal in the case that one of the following criteria applies:

- Prior bilateral oophorectomy, OR
- Age \geq 60 years, OR
- Age $<$ 60 years with intact uterus and amenorrheic for \geq 12 consecutive months **prior to** chemotherapy and/or endocrine therapy exposure

4.3.9. Tumor assessment

Patients must have measurable disease, defined as at least 1 unidimensionally measurable lesion as defined by RECIST v1.1 (tumor \geq 1 cm in longest diameter on axial image on CT or MRI, tumor \geq 10 mm by caliper measurement on clinical exam and/or lymph node(s) \geq 1.5 cm in short axis on CT or MRI). This includes lytic bone lesions or mixed lytic-blastic lesions with an associated soft tissue component \geq 10mm noted on CT or MRI as per RECIST v1.1. I. Index lesions cannot have been previously treated with local therapy, such as radiation.

Baseline imaging must be performed within 28 days of initiating therapy. Ideally, this will include a CT scan of the chest, abdomen, and pelvis with IV contrast, or can consist of an MRI of the chest, abdomen, and pelvis or

positron emission tomography (PET) scan with diagnostic non-contrasted CT of the chest, abdomen, and pelvis for patients who cannot undergo a contrast-enhanced CT scan. Bone scan will be done at screening and repeated only if clinically indicated or at the treating physician's discretion. If a patient has an allergy to IV contrast, appropriate pre-medication can be given to prevent a contrast reaction. Patients may undergo other modalities such as an MRI instead of a CT scan at the treating physician's discretion if appropriate (such as severe allergy to CT contrast, extremity tumors, bone metastases requiring bone scans, etc.).

Patients will receive therapy until disease progression, as per RECIST v1.1 criteria, or therapy intolerance. Response assessment will occur every 8 weeks (+/- 7 days), attempting to occur close to the start of a new cycle. If there are any significant delays, restaging exams must not occur more than 12 weeks (+/- 7 days) apart. For patients who achieve a CR, PR, or SD (as demonstrated by RECIST v1.1) confirmed on two consecutive restaging scans, restaging scans may transition to every 12 weeks. Re-staging CT scan of the chest, abdomen, and pelvis with IV contrast, MRI of the chest, abdomen, and pelvis, or positron emission tomography (PET) scan with diagnostic non-contrasted CT of the chest, abdomen, and pelvis will be repeated every 8 weeks (+/- 7 days), or 12 weeks (+/- 7 days) if the patient has achieved CR, PR or SD on two consecutive restaging scans. Bone scan is optional. Only patients with SD, PR, or CR, as demonstrated by RECIST v1.1 will continue on treatment per protocol.

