4.5. Study Activities Checklist

Screening

Eligibility Criteria	_____
Informed Consent	_____
Demographics	_____
Medical History	_____
Concomitant Medications	_____
Pregnancy Test	_____
Vital Signs	_____
Height	_____
Weight	_____
History and Physical	_____
Performance Status	_____
CBC with Differential	_____
Serum Chemistries (sodium, potassium, calcium, chloride, bicarbonate), BUN, creatinine, AST, ALT, total bilirubin, albumin, alkaline phosphatase)	_____
Lipid Panel (total cholesterol, LDL, HDL, and triglycerides)	_____
CT c/a/p with IV contrast or MRI or PET/CT (diagnostic CT)	_____
Bone scan (optional, at investigator discretion)	_____
Brain MRI (if history of brain metastases or current suspicious neurologic symptoms)	_____
Tumor Measurements	_____

Cycle 1, Day 1

Concomitant Medications	_____
Pregnancy Test (within 14 days of C1D1)	_____
Weight	_____
Vital Signs	_____
Interval History and Physical	_____
Performance Status	_____
Adverse Event Evaluation	_____
CBC with Differential (within 8 days)	_____
Serum Chemistries (sodium, potassium, calcium, chloride, bicarbonate), BUN, creatinine, AST, ALT, total bilirubin, albumin, alkaline phosphatase) (within 8 days)	_____
Dispense SM-88 and MPS	_____
Cell free DNA (cfDNA) collection (pre-treatment)	_____

Cycle 1, Day 15

CBC with Differential (+/- 3 days)	_____
Serum Chemistries (sodium, potassium, calcium, chloride, bicarbonate), BUN, creatinine, AST, ALT, total bilirubin, albumin, alkaline phosphatase) (+/- 3 days)	_____

Cycle 2, Day 1

Concomitant Medications	_____
Pregnancy Test (within 8 days)	_____
Weight	_____
Vital Signs	_____
Interval History and Physical	_____
Performance Status	_____
Adverse Event Evaluation	_____
CBC with Differential (within 8 days)	_____
Serum Chemistries (within 8 days)	_____
Cell free DNA (cfDNA) collection	_____
Study Drug Accountability	_____
Dispense SM-88 and MPS	_____

Cycle 2, Day 15

CBC with Differential (+/- 3 days)	_____
Serum Chemistries (sodium, potassium, calcium, chloride, bicarbonate), BUN, creatinine, AST, ALT, total bilirubin, albumin, alkaline phosphatase) (+/- 3 days)	_____

First Response Assessment (after 8 weeks on treatment, Cycle 3 Day 1)

Pregnancy test (within 8 days)	_____
Weight	_____
Vital Signs	_____
Concomitant Medications	_____
Interval History and Physical	_____
Performance Status	_____
Adverse Event Evaluation	_____
CBC with Differential (within 8 days)	_____
Serum Chemistries (within 8 days)	_____

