¹¹ End of Treatment visit should occur as soon as possible at the time of progression or discontinuation of treatment, preferably before the subject starts the next therapy, + 10 days from last dose. Imaging and tumor assessments do not need to be performed at this visit if performed within 30 days prior to the visit.

¹² Bone scan at investigator discretion

¹³ Long term follow up assessment (+/- 4 weeks). Patients will be contacted by phone call or e-mail for vital status data collection, adverse events evaluation (if AEs from study have not yet been closed), subsequent anti-breast cancer therapy (systemic therapy, radiation, or surgery), and development of a secondary malignancy.

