7.1.2.2. Non-measurable disease

All other lesions (or sites of disease), including small lesions (longest diameter <10 mm or pathological lymph nodes with ≥ 10 to <15 mm short axis), are considered non-measurable disease. Bone lesions, without associated soft tissue components, blastic bone lesions, leptomeningeal disease, ascites, pleural/pericardial effusions, lymphangitis cutis/pulmonitis, inflammatory breast disease, and abdominal masses (not followed by CT or MRI), are considered as non-measurable.

Note: Cystic lesions that meet the criteria for radiographically defined simple cysts should not be considered as malignant lesions (neither measurable nor non-measurable) since they are, by definition, simple cysts.

'Cystic lesions' thought to represent cystic metastases can be considered as measurable lesions, if they meet the definition of measurability described above. However, if non-cystic lesions are present in the same patient, these are preferred for selection as target lesions.

All measurements should be taken and recorded in metric notation, using a ruler or calipers. All baseline evaluations should be performed as closely as possible to the beginning of treatment and never more than 4 weeks before the beginning of the treatment. The same method of assessment and the same technique should be used to characterize each identified and reported lesion at baseline and during follow-up. Clinical lesions will only be considered measurable when they are superficial (e.g., skin nodules and palpable lymph nodes). For the case of skin lesions, documentation by color photography including a ruler to estimate the size of the lesion is required.

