7.4.1.3. Progressive Disease (PD)

At least a 20% increase in the sum of the LD of target lesions, taking as reference the smallest sum LD recorded since the treatment started, or the appearance of one or more new lesions, and/or an unequivocal progression of non-target lesions.

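### The plan both requires and waives the screening bone scan, so a bone lesion present before treatment can be recorded as progression when the first bone scan is done on treatment

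*Combined protocol and SAP*

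**What the plan says.** Four places in the current text deal with the screening bone scan.

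- Section 4.3.9: "Bone scan will be done at screening and repeated only if clinically indicated", or if the treating physician so chooses. The condition attaches to the repeat, not to the screening scan. The later sentence "Bone scan is optional" follows the restaging instructions and is naturally read as applying to restaging.
- Table 3, bone scan row: a plain X at screening. The marks at Cycle 3, every 8-12 weeks and End of Treatment are each labelled optional.
- Section 4.5, Screening block: "Bone scan (optional, at investigator discretion".
- Table 3, footnote 12, attached to the row label: "Bone scan at investigator discretion", with no restriction to visits after screening.

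On response, section 7.4.1.3 counts as progression "or the appearance of one or more new lesions, and/or an unequivocal progression of non-target lesions". Table 6 gives progressive disease for any new lesion, whatever the target lesions show, and sections 7.4.1.1 and 7.4.1.2 bar new lesions from complete and partial response. Section 7.1.2.2 classes as non-measurable "Bone lesions, without associated soft tissue components, blastic bone lesions, leptomeningeal disease", and section 7.2.1.2 expects all such sites to be recorded as non-target lesions at baseline.

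**The concern.** A lesion can be called new only against a baseline that would have shown it. If the bone scan is skipped at screening and done later, bone metastases that were present from the start can appear for the first time on treatment. The plan has no rule for classing such a lesion.

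A false progression has two effects. It is a PFS event under section 8.4.2.2, which relies on local assessment, and it takes the patient off treatment under section 4.3.12. Bone disease is to be expected in this population: bone metastases are provided for in the eligibility limits and supportive care sections, and measurable bone-only disease is eligible. Sites following different parts of the protocol would also measure progression against different baselines.

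**Working it through.** **1. Is the conflict real?** Section 4.3.9 and the Table 3 cell require the scan at screening; the section 4.5 checklist and footnote 12 make it discretionary. Table 3 thus disagrees with its own footnote. All four texts are current.

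**2. Can an old lesion become progression?** Each step is permitted by the documents:

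- A patient is enrolled under the checklist with no baseline bone scan.
- A bone scan is done on treatment, as section 4.3.9, the checklist and Table 3 all allow.
- The scan shows a bone lesion that the baseline imaging did not cover or did not reveal.
- The investigator, who applies RECIST under section 7.3, records a new lesion, which is progression under section 7.4.1.3 and Table 6.

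The same-method rule in section 7.2 does not break this chain. It governs lesions already identified and reported; it does not say how to class a lesion first seen by a method not used at baseline.

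**3. Which endpoints move?**

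- PFS: shortened by any false progression that comes before the true event.
- Duration of response: shortened when the false progression follows a response.
- Clinical benefit rate: lowered when the false progression comes before 24 weeks of benefit are reached.
- ORR: lowered only when the false progression comes before a confirmed response, because section 7.5 takes the best response recorded up to progression. Sections 7.4.1.1 and 7.4.1.2 require two observations at least 4 weeks apart. With scans every 8 weeks, a response first seen at week 8 would be confirmed on schedule at week 8 + 8 = 16. Section 1.5 reports that most best responses in the first-in-human study came after 3 months, so there is a window for this to happen.

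**4. Illustration for power.** Inputs from section 8.3: null ORR 0.095, alternative 0.20; 30 patients in stage 1, continue with 3 or more responses; 50 in total, success with 8 or more. With X1 ~ Bin(30, p) and X2 ~ Bin(20, p),

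P(success) = sum over x = 3 to 30 of P(X1 = x) × P(X2 ≥ 8 − x).

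The plan's own figures reproduce: 0.0955 at p = 0.095 (limit 0.10) and 0.802 at p = 0.20 (stated 0.8).

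If a share m of true responders is lost, p = 0.20 × (1 − m). The documents give no value for m, so these are assumptions. With 50 × 0.20 = 10 expected responders, the expected number lost is 10 × m.

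| m (assumed) | p | Responders lost of 10 | Power |
|---|---|---|---|
| 0 | 0.200 | 0 | 0.802 |
| 2% | 0.196 | 0.2 | 0.783 |
| 5% | 0.190 | 0.5 | 0.751 |
| 10% | 0.180 | 1.0 | 0.691 |

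**The case against.** **The baseline is not blind to bone.** Every patient has CT, MRI or PET/CT of the chest, abdomen and pelvis within 28 days before treatment, and all other sites of disease must be recorded as non-target. This stands, and it narrows the exposure mainly to bone outside that field and to lesions not visible on that imaging. It does not close the gap.

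**Bone-only eligibility adds little.** A reader might infer that patients with bone-only disease enter with their disease unmapped. The documents do not support that. Such disease qualifies only through a soft tissue component of at least 10 mm seen on CT or MRI, so the qualifying lesion is imaged at baseline. Only further bone lesions are at risk.

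**The power figures have no anchor.** A reader might take the table as an estimated loss of power, or conclude that the sample size is wrong. Neither follows. Several conditions must coincide before a responder is lost, and scans repeated for clinical indication may well fall less often on patients who are responding. The design reproduces as stated.

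**Unblinded assessment.** A reader might infer that open-label discretion favours the drug. In a single-arm trial there is no between-arm bias, and this error pushes ORR down, so it does not inflate the type I error.

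**Discretion may be what was intended.** The Version 1.3 log entry records the addition of the footnote wording, so section 4.3.9 could be the part left behind. The log does not settle this, but it means that alignment with 4.3.9 is not purely editorial for sites that followed the checklist.

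**Conclusion.** The inconsistency is established: two places require the screening bone scan and two waive it. It follows that a pre-existing bone lesion can be recorded as progression in a patient with no baseline bone scan, and nothing in the response rules prevents this.

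The effect is mainly a bias towards shorter PFS and duration of response and a lower clinical benefit rate. Its size is unknown. It depends on how many patients are enrolled without the scan, how many are scanned later, and how often an old lesion escapes the baseline imaging; the documents give none of these. ORR is affected only through false progression before a confirmed response. Power of 0.783, 0.751 or 0.691 describes assumed losses of 2%, 5% or 10% of true responders and should not be read as a forecast.

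**What to change.** 1. **Reconcile the four places.** Make the section 4.5 screening checklist and footnote 12 agree with the baseline scan already required by section 4.3.9 and marked in Table 3, and limit investigator discretion to repeat scans. The cost is protocol wording, plus a baseline scan at sites that had been following the checklist.

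2. **Patients already enrolled without a baseline bone scan.** Flag in the data any progression that rests only on a bone lesion first seen on bone scan. Report a sensitivity analysis of ORR, PFS, duration of response and clinical benefit rate in which such a lesion does not count as progression unless later imaging shows progression. The cost is one data item and one extra set of results. State the limits: patients leave treatment at recorded progression and the follow-up visits schedule no scans, so later imaging will often be missing and the censoring rule for that case must be written down. The analysis also cannot recover a response that treatment might still have produced.

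3. **Do not substitute a fixed classification rule in section 7.4.1.3.** It is tempting to say that such a lesion is never new unless baseline CT or MRI shows it was absent. Where that bone was not imaged at baseline, a genuinely new metastasis could then never count, which would bias PFS and ORR upwards. A lesion present but invisible on baseline CT would look absent and still be called new.
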